**Figure 2. Peer Coach Intervention Results in Increased Activated Self-Management**

The four key functions of peer support result in increased self-management in the four core domains of self-management and patient activation, as well as increased health related quality of life.

Baseline AYA and Ecological Characteristics are related to self-management outcomes and the intervention is tailored to support based on these varying characteristics.

**Table 7. Components of peer support intervention, AYA challenges, and peer coach support**

Components of Peer Support	Self-management challenge	Standard medical system approach	Nondirective peer coaching approach
Daily Management	Difficulty adhering to medication schedule	Provider instructs when and how to take medication	Coach helps explore daily routines; how medication schedules can link into daily routines; barriers to adherence
Social/emotional support	Following self-management plan when with peers	Altering therapy for flexibility (e.g. switching insulin pump in diabetes)	Coach helps explore fears of being different than peers; provides emotional support; role plays plan to talk to friends about condition
Providing linkage to clinical care	Attending regular clinic appointments	Clinic schedules appointments at regular intervals with reminders	Coach explores navigation of clinic system; how to reach out to schedule appointments; developing differing relationships with adult-care team
Providing ongoing support	Consistently follow self-management plan over time	Regular clinic visits with doctor and care team to monitor symptoms	AYA speaks with coach on regular basis over time; coach provides support to help consistently follow self-management plan and cope with stressors.

The peer coach will discuss daily management tasks (Key Function 1) during intake assessment and as part of the ongoing coaching process. The peer coach will also discuss the AYA's healthcare team and their ability to navigate the healthcare system. The peer coach will provide indirect linkage to clinical care by providing support to participants around goals related to healthcare navigation, while also communicating directly with the clinical team should the need arise. The circumstances by which the coach would share information with the clinical team are primarily related to safety concerns. The clinical team can also provide the coach with information regarding symptoms, treatments, and other relevant health information (Key Function 3). By providing support around daily management and the linkage to clinical care the peer coach promotes an increase in all the self-management domains and patient activation.

The social and emotional support (Key Function 2) and ongoing support (Key Function 4) are critical components within PICASO. AYAs will identify goals and through the coaching process may choose to focus on the social consequences or emotional challenges of coping with a COCC. The coach will use the nondirective supportive tools gained in their training to promote active coping and to provide nondirective emotional support. This type of support is associated with positive coping and with lower rates of depression/anxiety in response to an emotional stressor. In addition, the nondirective emotional support is expected to be related to the outcome of improved health-related quality of life.

The peer coaching interactions will occur using the InquisitHealth Mentor 1:1™ Web Based Portal. This platform designed by InquisitHealth and deployed commercially across multiple settings in which peer support is activated, facilitates interactions using telephone and a web-based peer-support interface. This informatics technology interface has been used successfully in a preliminary study of AYA with COCC, as well as for adults with chronic conditions. Through the software interface, the AYA and coach arrange times to speak according to the protocol schedule. They can exchange secure communication via phone and text messages, and coaches can send them monthly educational newsletters. The coaches will track the AYA's progress over time using the InquisitHealth web-based software. This database includes progress on key health behaviors discussed and notes the coaches submit after each session. Peer coaches and AYA will communicate by phone and text twice weekly over the first 16 weeks of the active relationship building phase. This will be followed by 18 weeks of weekly communication in the goal-focused phase. Last, peer coaches will have twice monthly communication for the final 18 weeks of the maintenance phase.

In general, calls last 20-30 minutes. During the first call, the coach and AYA have the opportunity to learn about one another's experiences with living with a chronic condition. During subsequent calls, the coach focuses primarily on the specific sub-behavior elected by the AYA. The coaching process model described in figure 2, helps the coach guide behavior change, beginning with assessing the participant's vision for the future, establishing focus, readiness to change, and then pursuit and maintenance of identified goals. As goal progress is made, the coach and AYA work to identify a new goal, or in the case of no progress, they discuss barriers and strategies, with an option to move on to another goal. Between sessions the coach and participant can exchange text messages including an update on progress towards a goal. At the end of the intervention the final call involves an opportunity for closure and for the coach and AYA to review progress on goals and future steps.

Attention Control: Over 12 months the attention control group participants will receive a monthly electronic newsletter with educational content about COCC management and the differences between pediatric and adult health care systems, as well as a monthly phone call from study staff to ensure receipt of the newsletter and to answer questions regarding content, and an opportunity to link them to other resources. If participants report health concerns they will be directed to contact their health care team.

Treatment fidelity and protocol adherence: See Human Subjects and Clinical Trials Information Section 4.2.a.13 and 4.3 for complete details on intervention fidelity, participant adherence, and adherence measurement. The NIH Treatment Fidelity Workgroup statement will guide our fidelity plan and Co-PI [name] has experience implementing these guidelines in a previous RCT intervention with adolescents undergoing blood and marrow transplant. Fidelity will be enhanced by the InquistHealth Mentor1to1™ platform which enables masked, direct voice communication; facilitates continuity of relationship between the AYA and peer coach; and allows for the systematic tracking of phone- and text-based interactions. After the call, the platform facilitates scheduling upcoming calls, automates text message and e-mail reminders, and allows for user-initiated text messaging between calls. Since all calls are facilitated through the platform, the system automatically tracks call length and frequency, and records these interactions. AYA engagement will be tracked and quantified by the number of contacts and average length of contacts time per week. These two numbers will be aggregated and plotted for each AYA. Together with weekly content analyses of a random selection of two calls and text messages from each coach, we will monitor AYA engagement and during biweekly coach training sessions address problems that arise. Fidelity will be assessed by examining peer

coach engagement and content of the call recordings. Peer coach engagement will be evaluated using the aggregated number of contacts and length of contact time for each of the 12-15 coaches. This will allow us to assess the extent to which coaches are engaged and to explore the reasons for increases or decreases in engagement. These evaluations will be performed weekly and feedback given to the peer coaches at the biweekly training sessions so that adjustments to the content/direction of the calls and text messages may be made by the coach at the subsequent call. A log will be kept of these assessments and any subsequent adjustments.

#### Aim 1 and 2 Analysis Plan

Descriptive statistics will be used to detail the sample characteristics of the (a) coaches and randomized AYAs and (b) detail the study outcomes for the AYAs at the five-assessment point (baseline, 3-, 6-, 9-, 12-months post randomization). Non-directional statistical tests will be performed, with the significance level set at 0.05 for each test. The significance level will not be adjusted for multiple outcomes and tests (see Power section below). Estimated effect sizes and their 95% confidence intervals (CI) will be reported to address magnitude of effect and clinical significance for the efficacy and moderator analyses (Aims 1 and 2, respectively).

**AYA Sample Characteristics.** Chi-square/Fisher's Exact Tests for categorical variables and General Linear Models (GLM) for continuous measures will be used to test for group (PICASO vs attention control) differences in the baseline demographic and clinical characteristics as well as baseline outcome measures for the AYAs. A GLM approach, which calculates least square means to adjust for unequal sample sizes, will be used to test for between-group differences in the means for continuous measures. Any significant between-group difference in a baseline characteristic detected will be evaluated as a potential covariate in the efficacy analyses

**Aim 1 Efficacy Analyses.** To test the efficacy of the PICASO compared to the attention control condition on the primary and secondary outcomes across the five assessment points (time), we will use a type of hierarchical mixed-effect model for longitudinal data known as random coefficients regression models (RRM) to evaluate group differences in the trajectory of change in each outcome across time. Fixed effects will be group, time, group-by-time, while random effects will be participant and participant-by-time. Potential covariates will be included as fixed effects and will be retained in the final model only if significant at the 0.05 level. When needed, the model will be fitted for any non-linear temporal effects observed. The assumption of data missing at random will be evaluated, and imputation for missing data will be applied when appropriate. Descriptive statistics will be used summarize the unadjusted and adjusted means at each assessment point. If there is a significant group-by-time interaction, *a posteriori* contrasts will be performed to compare the two groups at each time point. For each outcome, the primary analysis will be an intention-to-treat (ITT) analysis in which all AYAs randomized will be included in the analysis. Supplemental analyses will be conducted on those AYAs who complete the 12-month assessment. Both ITT and completers' results will be reported.

**Aim 2 Moderator Analyses.** To explore whether age, biological sex, race/ethnicity, chronic condition, and/or disease severity moderate the trajectory of PICASO effects on the primary and secondary outcomes, the trajectory analysis approach described in Aim 1 will be used to evaluate the moderating effects of each candidate moderator on each outcome. Each candidate moderator will be evaluated separately by incorporating the variable (e.g., age) and its interaction with group and time as fixed effects in the model for each outcome. By definition, a significant candidate moderator-by-group-by-time interaction would indicate that the variable moderates the effects of the PICASO compared to the control group over time. If a moderator interaction is significant at the 0.05 level, the RRM core model applied in Aim 1 will be fitted for subgroups of the moderator to better determine the differential trajectory of change from baseline to 12-month within each moderator subgroup. This analytic method will be applied in accordance with recommended approaches for assessing moderator effects in trajectory and/or growth models.

**Aim 3:** Explore mechanisms of PICASO impact by describing AYA experiences with the intervention and the InquisitHealth Mentor 1:1™ Web Based Portal. Aim 3's goal is to understand intervention mediators by characterizing how intervention components, as well as the unique case context of their use, may (a) target (or miss) within-case needs, (b) address variability across chronic condition and age contexts, and (c) impact patterns in outcome measures. **Approach & goal:** We will integrate findings from qualitative interviews with AYA outcomes. This mixed methods analysis will provide insight into intervention mediators (mechanisms of action) and highlight how outcomes may be related to unique case contexts; both of which will lead to future intervention optimization through enhanced personalization, replicability, and scalability.

**Aim 3 Mixed Methods Analyses.** We will explore AYA experiences with the PICASO using a mixed methods approach to characterize participants' experiences with the intervention to understand mechanisms of action, how outcomes may be related to unique case contexts, and if barriers to broader implementation and dissemination are perceived. This knowledge will also guide future intervention optimization through enhanced

personalization, replicability, and scalability. Interview transcripts will be analyzed using a content qualitative analysis technique that combines structural (e.g., intervention component, transition barriers) and magnitude coding (e.g., theme intensity) with inductive coding (e.g., variations in outcomes not captured by instruments). Drs. [name] and [name] will separately code 10 interviews, discuss the generated codes, and create an initial code book by consensus. The code book will then be used by CRC coders for the next 10 transcribed interviews (with [name] coding each 5th interview), with further refinements made as needed. The final code book will be organized into categories used to generate themes of mechanistic and process elements. The qualitative content analysis findings within each case will then be integrated with the relevant quantitative questionnaire- and informatics-based data. A matrix will be constructed to display case findings (qualitative data in relation to quantitative data) in relation to every other case. This will allow a cross-case comparative analysis, with the possibility of conducting an even wider range of theoretically driven analyses. For example, case comparisons could be made by diagnostic category or mentor condition match. Next, process tracing will be used to explore how particular case outcomes (e.g., self-management, coping, self-esteem) may have been related to intervention components (e.g., goal selection, strategies). [name] will use ATLAS.ti software to aid in coding and organizing transcribed interviews and field notes.

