**Table 5. Sample**

Condition Category	Diagnoses	N	Peer Coach
1. Frequent Hospitalizations or ED visits	Sickle Cell Disease; Chronic Kidney Disease, Lupus	50 PICASO 25 control	4-5
2. High daily management with intermittent flares	Type 1 Diabetes Mellitus; Inflammatory Bowel Disease; Severe Asthma	70 PICASO 35 control	5 -6
3. Survivor of life-threat condition requiring ongoing symptom mgmt	Stem Cell Transplant, Organ Transplant, Cancer Survivor	30 PICASO 15 control	3-4
Total: 150 PICASO / 75-control 2:1 ratio			12-15

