### **3.D.4.a. Study Procedures by Specific Aim**

**Aim 1:** Determine the efficacy of the PICASO on primary outcomes (self-management, patient activation) and secondary outcomes (transition readiness, health-related quality of life, emotional health) across 12 months.

**Aim 2:** Explore moderators of trajectory of PICASO effects on self-management, patient activation, transition readiness, health-related quality of life and emotional health across 12 months.

Overview and design: We will test the hypothesis that compared to an attention control group, the PICASO group will improve self-management and patient activation as well as improve secondary outcomes (transition readiness, HRQoL, emotional health) in a RCT over 12-months with 225 AYAs with COCC. The primary outcomes are the post-intervention scores on the Partners in Health Scale and the Patient Activation Measure.

Recruitment plan: Our detailed Recruitment and Retention Plan is provided in [Human Subjects and Clinical Trials Information Section 2.5](#); a brief summary follows. Participants will be recruited by the study CRC in partnership with the Duke Children's Health Center ambulatory clinic staff (attending physicians, fellows, and nurse practitioners - see Letters of Support from Clinic Medical Directors). At the end of each week clinic staff and the CRC will review lists of AYAs scheduled for appointments the following week. Eligible AYA will be identified and flagged to be provided with basic information about the study by the clinic staff the following week. If an AYA and parent/guardian (for those less than 18 years) express an interest in the study, the CRC will meet with them at the same appointment for study introduction. Once questions have been answered the informed consent process will be conducted by the CRC in a confidential manner.

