Randomization and data collection (detail in [Human Subjects and Clinical Trials Information Section 4.2.a.7 & 4.2.a.11](#)): On completion of baseline data collection, AYAs will be randomized using a stratified randomization with permuted block sizes of four to either the PICASO intervention (N=150) or attention control group (N=75). While stratifying on condition category, a 2:1 treatment allocation will be applied to ensure as an intervention sample size that is sufficient to provide robust findings and increase the precision of the outcome parameter estimates for the PICASO intervention. A RedCAP data base platform will be used to administer the randomization scheme prepared by the study statistician.

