### **3.C.8. Sample Size and Power Considerations**

A target sample size of 225 AYAs (PICASO: N=150; control: N=75) will be provide at least 80% statistical power to address the efficacy of PICASO compared to the attention control condition (Aim 1) and will provide sufficient heterogeneity to obtain reliable estimates of effect sizes for the exploratory moderator analyses. Using PASS software (NCSS LLC, Kaysville, UT), the sample size determination for the two primary outcomes was based on the following assumptions: (a) mixed-effects trajectory analyses using RRMs; (b) two-tailed tests with significance set at 0.05 per test; and (c) medium effects (Cohen  $d$  equivalent of 0.50); and (d) unstructured within-subjects correlation patterns over time. The significance level of 0.05 will not be adjusted for evaluating two primary outcomes. Although the mixed-effects models allow for data missing at random, the sample size of 225 takes into account an attrition rate of up to 20% over time, and thus, should provide 80% power for both the ITT and completers' analyses of the two primary outcomes.

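### The Aim 1 model leaves out the randomisation stratum and chooses its covariates by p-value, so it is not fixed in advance; the cost is small and conservative, and the fix is free

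*Combined protocol and SAP*

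**What the plan says.** Section 3.D.4.a (Randomization and data collection) allocates 225 participants 2:1 in permuted blocks, "While stratifying on condition category". Table 5 plans three categories at 50:25, 70:35 and 30:15 and ends with "Total: 150 PICASO / 75-control 2:1 ratio".

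The Aim 1 and 2 Analysis Plan gives the efficacy model: "Fixed effects will be group, time, group-by-time, while random effects will be participant and participant-by-time". Covariates can enter in two steps. Baseline variables, baseline outcome measures among them, are tested between arms, and "Any significant between-group difference in a baseline characteristic detected will be evaluated as a potential covariate in the efficacy analyses". Then "Potential covariates will be included as fixed effects and will be retained in the final model only if significant at the 0.05 level". No covariate is named beforehand. Chronic condition is modelled only in the exploratory Aim 2 analyses: "Each candidate moderator will be evaluated separately by incorporating the variable (e.g., age) and its interaction with group and time as fixed effects".

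Section 3.D.4.a also states: "The primary outcomes are the post-intervention scores on the Partners in Health Scale and the Patient Activation Measure". The Analysis Plan instead tests group-by-time, and compares the arms at each visit only when that interaction is significant.

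**The concern.** Three things are unsatisfactory.

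- **The stratum has no place in the model.** Stratified randomisation removes between-category variation from the treatment comparison. An analysis that ignores the strata leaves that variation in the estimated standard error, which is then too large. The covariate rule cannot repair this, because it looks for imbalance and the stratum is balanced by design, however prognostic it may be.
- **The covariates are chosen from the data.** In a randomised trial baseline differences arise by chance, so an imbalance test does not pick out prognostic variables. Which adjusted estimate is reported for each primary outcome is settled after the data are seen, and the two outcomes can end up with different covariates.
- **A baseline score could be used twice.** Baseline is already the first of the five responses. The wording permits, though it does not state, that a flagged baseline score also becomes a covariate.

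At stake are some precision in time-point comparisons and the claim that the primary model was set in advance. Inflated type I error is not the worry.

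**Working it through.** **Inputs from the documents.** 150 vs 75 participants; d = 0.50; "two-tailed tests with significance set at 0.05 per test"; attrition up to 20%, which leaves 120 vs 60 (section 3.C.8). Strata of 75, 105 and 45 (Table 5).

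**Assumed.** The share of outcome variance explained by the stratum, R², is not given. I use 2%, 5% and 10%. Section 3.D.3.c says that diagnostic groups vary more within than between, which favours the low end.

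**1. The plan's own figure.** As a simple comparison of two means with SD 1, power = Φ(d/√(1/n₁ + 1/n₂) − 1.960).
- 150 vs 75: 0.50/0.1414 = 3.536, and Φ(1.576) = 94.2%.
- 120 vs 60: 0.50/0.1581 = 3.162, and Φ(1.202) = 88.5%.

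The claim of at least 80% is met with margin. The exact mixed-model figure cannot be rerun, because no correlations are given.

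**2. Can the screen reach the stratum?** On the planned 50:25, 70:35 and 30:15 split, the chi-square of arm by category has p = 1.0. In 20,000 simulated trials with random stratum sizes it was flagged in none; the smallest p was 0.95 with blocks of 3 and 0.85 with blocks of 6. (The protocol's blocks of four cannot hold an exact 2:1 split, so block sizes that can were used.)

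**3. Cost for a single 12-month score.** With balanced strata the standard error is overstated by f = 1/√(1 − R²). Type I error becomes 2[1 − Φ(1.960 f)]: at R² = 10%, f = 1.054 and the result is 0.039. Simulation with 60,000 runs per cell (Monte Carlo SE √(0.05 × 0.95/60,000) ≈ 0.001) gave:

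| R² | f | Type I error, stratum omitted: 225 / 80% retained | Power, omitted → included: 225 | Power, omitted → included: 80% retained |
|---|---|---|---|---|
| 2% | 1.010 | 0.047 / 0.048 | 94.3% → 94.5% | 88.4% → 88.8% |
| 5% | 1.026 | 0.044 / 0.045 | 94.4% → 95.0% | 88.4% → 89.5% |
| 10% | 1.054 | 0.038 / 0.041 | 95.0% → 96.0% | 89.0% → 91.0% |

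With the stratum in the model, type I error was 0.049 to 0.051.

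**4. Cost for the group-by-time test.** Per-participant slopes over the five visits were used as a stand-in for the mixed model, with complete data and assumed variances of 0.6 (intercept), 0.3 (slope) and 0.4 (residual).
- Stratum affects level only (R² 5%, 10%): type I error 0.050 and 0.049, SE ratio 1.000.
- Stratum also explains 5% or 10% of slope variance: 0.049 and 0.046, SE ratios 1.008 and 1.016.

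**5. Five-visit mixed model.** Complete data, 1,500 runs, stratum R² 10%, assumed variance components 0.6, 0.3 and 0.3, 12-month difference 0.4.
- Group-by-time power: 81.6% with no covariates, 81.6% under the two-step rule, 81.1% with a stratum main effect, 82.9% with stratum-by-time added.
- 12-month contrast power: 64.9% with no covariates, 65.7% under the two-step rule, 70.2% with the stratum. Type I error: 0.038, 0.030 and 0.047. The Monte Carlo SE is √(0.05 × 0.95/1,500) ≈ 0.006, so these type I figures are rough.

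**6. The two-step rule.** The chance that at least one of K independent baseline variables is flagged is 1 − 0.95^K: 23% for K = 5, 40% for K = 10, 54% for K = 15. Simulation with K = 5 or 10, each covariate explaining 1–5% and an outcome residual correlation of 0.5 (all assumed; 8,000 runs per cell) gave at least one flag in 23–41% of trials, a changed final model in 8–38%, different covariate sets for the two primary outcomes in 3–12%, and type I error of 0.038–0.053 (Monte Carlo SE about 0.002).

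**The case against.** The strongest reply is that the planned Aim 1 test is group-by-time, and on that test omitting the stratum does almost nothing. Visit-by-visit contrasts come only after a significant interaction. This stands for the slope test. It does not dispose of the point, because section 3.D.4.a calls the post-intervention scores the primary outcomes and the contrasts are part of the plan.

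Second, every magnitude rests on an assumed R², and the protocol's own reading of the literature suggests a weak stratum. This also stands: at 2% the loss is 0.2 to 0.4 points of power, against a calculation that already exceeds 80%.

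Third, the selection rule is itself written down in advance, the core terms are fixed, unadjusted and adjusted means will both be summarised, and no type I inflation appears. That is fair. But the simulations apply the rule mechanically, whereas the plan says only that a flagged variable will be evaluated, which leaves discretion. A changed covariate list is also a changed estimate, even if the conclusion usually survives.

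Fourth, the covariate sentence may be meant to exclude baseline outcome scores. That is possible, and the plan should say so.

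Finally, the Human Subjects sections that the protocol cites for randomisation detail are not in the public document and might add something. In the text available, neither they nor the exploratory moderator models give the stratum a place in Aim 1.

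**Conclusion.** The point holds at a modest size. The model does not reflect the stratified randomisation, the stated covariate route will essentially never bring the stratum in, and the remaining covariates depend on chance imbalance.

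For a single 12-month score, with R² of 2–10%, omission makes the test slightly conservative (type I error down to about 0.04) and costs 0.2 to 1.0 points of power with all 225, or 0.4 to 2.0 points at 20% attrition. These figures sit near the power ceiling. In the five-visit model, at a smaller effect and R² of 10%, the 12-month contrast lost about 5 points (70.2% − 64.9%). A loss of about 12 points needed R² of 20% on both level and slope, which the protocol's own remarks make unlikely. The group-by-time test is nearly unaffected unless the stratum predicts slope.

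The weightier part is that the primary model is not fixed in advance. The rule also forgoes precision: with covariates explaining 30% of variance (assumed), 12-month power at d = 0.50 was 89.5% under the two-step rule and 96.2% with those covariates named beforehand. None of this threatens the trial's validity or its stated power.

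**What to change.** Replace the test-and-retain rule in the Aim 1 and 2 Analysis Plan with wording such as: *Condition category (the randomisation stratum) and its interaction with time are fixed effects in every Aim 1 model. Any other covariates are listed before unblinding and kept whatever their p-values. The baseline outcome is not entered as a covariate in a model where it is also a response.* The interaction with time is included because only that term can help the slope test. Baseline comparisons between arms may still be reported descriptively, but should not drive covariate selection.

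The cost is a change of wording. Condition category is already recorded at randomisation. With linear time the model gains four fixed-effect parameters (two for category, two for category-by-time) among 225 participants. No extra participants or data are needed.

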**Table 6. Overview of eligibility criteria**

Inclusion
1. AYA 16 to 22 years
2. Childhood onset chronic condition from 1 of 3 condition categories (see Table Y).
3. Read and speaks English
4. Access to internet via computer or Smart Phone
4. Access to telephone (Smart Phone not required as text feature can be accessed via internet)
Exclusion
1. Diagnosed cognitive dysfunction
2. Need for English translator

**3.D.3.d. Outcome measures.** Study outcomes are described in detail in [Human Subjects and Clinical Trials Information Section 4.3](#). All outcomes have been piloted by our team and chosen based on the conceptual model, expert recommendations, and psychometrics. Response burden will be minimized with short instruments and online data entry via REDCap survey. Pilot testing confirmed completion times ranging from 15-20 minutes.

Primary outcome measures. The constructs of (a) self-management and (b) patient activation will be assessed at baseline, 3-, 6-, 9-, and 12-months post randomization. Self-management will be measured using the Partners in Health Scale (PIH), assessing chronic condition self-management knowledge, partnership in treatment, recognition and management of symptoms, and coping. Patient activation will be measured using the Patient Activation Measure (PAM). The PAM measures patient activation through self-reports of knowledge, skills, and confidence related to self-management of one's own health care.

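### The declared primary outcome is a post-intervention score, but efficacy is decided by a group-by-time test whose time form is left open and which gates the month-12 comparison

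*Combined protocol and SAP*

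**What the plan says.** **Declared outcome.** The overview and design text of Section 3.D.4.a states: "The primary outcomes are the post-intervention scores on the Partners in Health Scale and the Patient Activation Measure". It names no month. The contact schedule in the same section runs 16 + 18 + 18 = 52 weeks and ends with "twice monthly communication for the final 18 weeks of the maintenance phase". Section 3.D.3.b also describes a 12-month intervention, so month 12 is the natural reading. It remains an inference. Section 3.D.3.d says "Study outcomes are described in detail in" a Human Subjects section, which was not supplied and may define the time point.

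**Deciding test.** The Aim 1 Efficacy Analyses use a random coefficients model "to evaluate group differences in the trajectory of change in each outcome across time", with fixed effects for group, time and their interaction. Arms are compared at individual time points, as a posteriori contrasts, under a condition: "If there is a significant group-by-time interaction". On the form of time the plan says: "When needed, the model will be fitted for any non-linear temporal effects observed". It gives no criterion, no candidate forms and no degrees of freedom for the interaction test.

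**Related text.** Table 3 lists a posteriori comparisons at each assessment point without stating the condition. The Aim 1 and 2 Analysis Plan adds: "Estimated effect sizes and their 95% confidence intervals (CI) will be reported to address magnitude of effect and clinical significance", without naming a time point. Adjusted means at each visit are promised descriptively. Section 3.C.8 bases power on "mixed-effects trajectory analyses using RRMs" and a Cohen d of 0.50, without saying whether d is a month-12 difference or a slope.

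**The concern.** Two parts of the plan point to different deciding quantities: a score at the end of the intervention, and the shape of change over five visits. They coincide only if the effect grows in a straight line and is modelled that way. The plan allows another form without saying what would trigger it.

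Two analysts who both follow the plan could therefore fit different time forms to the same data and reach different conclusions on efficacy. With a non-linear form, a non-significant interaction would also leave the month-12 difference without a formal test of its own.

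**Working it through.** **Inputs from the plan.** 150 PICASO and 75 control; attrition up to 20%, leaving 120/60; visits at months 0, 3, 6, 9 and 12; two-sided 0.05; d = 0.50 (Section 3.C.8; Section 3.D.3.d).

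**Assumptions (not in the documents).** SD 1 at every visit; correlation exchangeable 0.5, exchangeable 0.7, or AR(1) 0.8 per visit; covariance known. Between-arm differences by visit: linear (0, .125, .25, .375, .5), plateau (0, .5, .5, .5, .5), delayed (0, 0, .1, .3, .5).

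**Step 1: the plan's own figure.** The power calculation cannot be rerun, because the correlations, time form and tested contrast are not given. As a single-visit benchmark, 80% power at 2:1 needs 48 + 96 = 144, and 144/0.80 = 180. At 120/60 the standard error is √(1/120 + 1/60) = √0.025 = 0.158, so z = 0.5/0.158 = 3.16 and power is Φ(3.16 − 1.96) = 88.5%. At 150/75 it is 94.2%. Neither contradicts the claim of at least 80%.

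**Step 2: interaction test, exchangeable 0.5, 120/60.** Code visits −2 to 2.
- Slope variance: 0.025 × 0.5/10 = 0.00125; standard error 0.0354 per visit.
- Straight line, linear effect: slope 0.125, z = 3.54, power 94%. Over four intervals the slope gives 4 × 0.125 = 0.50, the true month-12 difference.
- Straight line, plateau: slope (−0.5 + 0 + 0.5 + 1.0)/10 = 0.10, z = 2.83, power 81%. Over four intervals it gives 0.40, not 0.50.
- Quadratic (2 df): the curvature contrast (2, −1, −2, −1, 2) is −1.0 for the plateau and 0 for the linear effect. Noncentrality for the plateau is (1.0²/10 + 1.0²/14)/0.0125 = 13.7, power 92%. For the linear effect it is (1.25²/10)/0.0125 = 12.5, power 90%.

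| True effect | Correlation | Straight line | Quadratic |
|---|---|---|---|
| Plateau | exchangeable 0.5 | 81% | 92% |
| Plateau | AR(1) 0.8 | 82% | 98% |
| Linear | exchangeable 0.5 | 94% | 90% |
| Linear | AR(1) 0.8 | 83% | 74% |

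The AR(1) rows come from simulation (400,000 draws). Neither form is better throughout.

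**Step 3: month-12 test accounting for baseline.** The variance is 0.025(1 − ρ²), where ρ is the baseline to month-12 correlation: 0.5, 0.7, or 0.8⁴ = 0.41. Then z = 3.65, 4.43 or 3.47, and power is 95%, 99% or 93%, whatever the path to month 12. By simulation across the three shapes and three correlations:

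| Sample | No gate | Behind a straight-line gate |
|---|---|---|
| 120/60 | 93–99% | 80–99% |
| 150/75 | 97–99.9% | 88–99.8% |

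**Step 4: type I error.** With no true effect, a month-12 difference is declared through a straight-line gate in about 2.1–2.5% of trials, so the gate does not inflate error. If the form were chosen on group-by-time curvature, the interaction test would reject in 7.2–7.3%. If it were chosen on the pooled time curve, it would reject in 5.0%. The documents state neither rule.

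**The case against.** The strongest reply is that trajectory is plainly the efficacy question. The Aim 1 hypothesis is about improvement over 12 months. Table 3, the Aim 1 and Aim 2 analyses and Section 3.C.8 all speak of trajectories. One sentence in Section 3.D.4.a is the outlier and may be loose wording. This largely stands: whether month 12 or trajectory is primary is the sponsor's decision, and amending that sentence is the smaller correction. It does not settle the form of time.

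Second, with straight-line time the interaction coefficient times 12 months is the model-based difference in change to month 12. This also stands. A reader might infer that the declared primary outcome goes untested altogether; the documents do not support that. The gap opens only when time is non-linear, which the plan permits. Effect sizes with confidence intervals and descriptive means are planned without the gate, so only formal testing is conditional.

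Third, the gate may cost little. At 150/75, closer to the planned intention-to-treat analysis, power behind a straight-line gate is at least 88% in every case above. Under exchangeable 0.7 the loss is small: at most about 4 points at 120/60.

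Fourth, the AR(1) figures assume a known covariance rather than the plan's random intercept-and-slope structure. Under that structure the straight-line plateau figure falls from 82% to 62%. The illustration depends on the working model.

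**Conclusion.** The mismatch is real and should be corrected, though it is modest in size. The declared outcome and the deciding test are not aligned, and the form of that test may be settled after the data are seen. In the assumed cases, the choice between straight line and quadratic moves power by 11 to 16 points one way for a plateau and by 4 to 9 points the other way for a linear effect. The cost of the gate ranges from almost nothing to about 15 points at 120/60 (95% against 80%: plateau, exchangeable 0.5).

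These sizes rest on assumed correlations, effect shapes and known covariance. Month 12 is inferred, and the unsupplied Human Subjects section may name the time point; that alone would not remove the gate or fix the form of time. A reader might also infer that the trial is underpowered or that its error rate is inflated. Neither is shown: the power claim is consistent with the benchmark, and the 7% figure needs a selection rule the documents do not state.

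**What to change.** Before unblinding, make Section 3.D.4.a and the Aim 1 Efficacy Analyses agree on one primary test per outcome. Either:

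- **(a) Month 12 primary.** Estimate and test the month-12 between-group difference from the longitudinal model in all randomised participants, with baseline accounted for and time categorical, whether or not the interaction is significant. Make the trajectory test secondary.
- **(b) Trajectory primary.** Amend Section 3.D.4.a to say so, fix the form of time in advance, and report the month-12 difference with its 95% CI whatever the interaction shows.

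In either case, take the data-driven choice of time form out of the deciding test, bring Table 3 into line, and state in Section 3.C.8 which contrast d = 0.50 describes.

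The cost is wording only: same data, visits and sample size. Option (a) loses power if the effect fades. With differences (0, .5, .5, .4, .3) at 120/60, the month-12 test has 55–76% against 87–98.5% for a quadratic trajectory test. Under option (b), power depends on the form chosen: a straight line has only 29–45% in that same case.
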